7.11 Vital Signs

Systolic and diastolic blood pressure, pulse rate, and respiratory rate will be measured at Visit 1 (Enrollment Visit) and Visit 2 (Allocation Visit). All vital signs will be measured in a sitting position after resting for 10 minutes. While resting, the subject should not receive anything to drink or eat.

7.12 Prior and Concomitant Medications

Verbatim terms on case report forms will be mapped to Anatomical Therapeutic Chemical (ATC) class and Generic Drug Names using the World Health Organization (WHO) dictionary (version March 2016).

For the purposes of data reporting by the site, all medications used 14 days prior to enrollment and up to the time of surgery are considered prior medications. Concomitant medications are all medications not stopped before start of surgery or newly added thereafter. Prior medications and concomitant medications will be summarized separately for each treatment by WHO ATC level 1 term, ATC level 3 term and generic drug name, with frequency and percentage of subjects in each dosing arm using each prior medication and each concomitant medication. At each level of subject summarization, a subject is counted once if he/she reported one or more medications at that level. Each summary will be ordered alphabetically by each level of ATC class and by generic drug name within each level of ATC class. Prior and concomitant medications will also be listed separately with these elements as well as the verbatim drug name.

The overall summary and subsets of prior and concomitant medications will be provided for the Safety Set, FAS and PPS.

8. EFFICACY ANALYSES

8.1 Efficacy Variables

8.1.1 Primary Efficacy Variable

The primary endpoint of the trial is 4-hour Total Pain Relief (TOTPAR4). TOTPAR4 is a time-weighted measure of Area under the Longitudinal Pain Relief Curve (AUC) up to 4 hours and is a summary measure that integrates serial assessments of a subject's pain over the duration of 4 hours after first dose (in [Appendix A](#)).

In general, the Total Pain Relief (TOTPAR) from the first administration of IMP to a fixed time-point, j , will be defined as:

$$\text{TOTPAR}_j = \sum W_i * \text{PR}_i, \text{ with } i \leq j$$

where the \sum sums over all observations collected from 0.25 hours after first IMP administration to Hour j and W_i is the time elapsed from the previous observation of pain relief PR_{i-1} to the current observation PR_i . For example, The TOTPAR4 will be calculated as a weighted sum of the observed pain relief scores for the first 4 hours after first dose with weights proportional to the duration of time since the last pain relief assessment.

For the first pain relief assessment, time (hours) elapsed since previous observation is time since first dose of IMP. Pain relief assessments after start of rescue medication intake will be set to missing and will be imputed as described in Section 8.3.

Minimum and maximum potential value for TOTPAR4 are 0 and 16 points, corresponding to a value of 0 (none) or 4 (complete) at all pain relief assessments in the first 4 hours after first dose, respectively.

8.1.2 Secondary Efficacy Variables

The following secondary clinical endpoints will be evaluated:

- Total Pain Relief at 6 hours (TOTPAR6), 8 hours (TOTPAR8) post-dose (in [Appendix A](#))
- Summed Pain Intensity Difference (SPID) at 4, 6, 8, and 24 hours after first dose (in [Appendix A](#))
- Time to achieve a 50% reduction of baseline pain (pain at least half gone) (in [Appendix A](#))
- Time to onset of first perceptible pain relief (stopwatch 1) (in [Appendix A](#))
- Time to onset of meaningful pain relief (stopwatch 2) (in [Appendix A](#))
- Time to intake of first rescue medication dose (in [Appendix A](#))
- Subject's global evaluation of the treatment (5-point Likert Scale; 0 poor to 4 excellent) at 8 hours after the first dose of IMPs or before first intake of rescue

medication (whichever was first) and at 24 hours after the first dose of IMPs (in [Appendix A](#))

Total Pain Relief (TOTPAR) is defined as $\sum PR_t \times$ [time (hours) elapsed since previous observation] where PR_t is the Pain Relief at time point t (based on VRS) in comparison to the assessment before administration of IMPs. The subject's pain relief is assessed using a 5-point Verbal Rating Scale (VRS) by completion of the following statement, "My relief from starting pain is" with the scale: 0 None; 1 A little; 2 Some; 3 A lot; 4 Complete.

Summed Pain Intensity Difference (SPID) is defined as $\sum PID_t \times$ [time (hours) elapsed since previous observation] where PID_t (Pain Intensity Difference) is defined as the difference between baseline pain intensity and pain intensity at time point t (e.g., baseline score - time point t score), where pain intensity is evaluated using an 11-point numerical rating scale (NRS) (in [Appendix A](#)).

8.1.3 Additional Efficacy Outcomes

The following parameters will also be summarized:

- Pain relief score after first dose over time (in [Appendix A](#))
- Pain intensity score after the first dose over time (based on NRS) (in [Appendix A](#))
- Pain Intensity Difference (PID, NRS) after first dose over time (in [Appendix A](#))
- Peak pain relief score
- Peak pain intensity difference score
- Time to request the first dose of rescue medication (in [Appendix A](#))
- Time to peak pain relief score
- Time to peak pain intensity difference score

Pain relief, pain intensity, and PIDs are defined as described above in Section 8.1.2.

The peak pain relief score is the maximum pain relief assessment for the subject during the 16 observation period (prior to the use of any rescue medication), while time to peak pain relief score is the time from first administration of IMP to the first occurrence of that peak relief score, in hours. The peak pain intensity difference is the maximum pain intensity difference for the subject during the 24 observation period (prior to the use of any rescue medication), while time to peak pain intensity difference is the time from first administration of IMP the first occurrence of that peak intensity difference, in hours.

8.2 Adjustments for Covariates

The primary analysis model will be an analysis of covariance (ANCOVA) with baseline pain intensity as a continuous covariate based on an 11-point scale), and treatment and site as factors. Baseline pain intensity will be included to ensure an equal distribution of subjects with severe baseline pain among the 4 treatment groups.

8.3 Handling of Dropouts or Missing Data

Diligent attempts will be made to limit the amount of missing data in the pain relief assessments used to determine the primary efficacy endpoint. Efforts will be made to encourage but not to enforce subjects to not start rescue medication intake if not needed. Assessments with missing date/time of evaluation will be considered unreliable and removed from all analyses and treated as missing values. Assessments made after the subject's first dose of rescue medication will be considered missing values and excluded from the analyses. Other than the methods outlined below for TOTPAR4, TOTPAR6, and TOTPAR8, no imputations will be performed to replace missing values for any of the other endpoints; those missing values will be left as missing.

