1.4.2 Rescue medication

Subjects will be encouraged to wait for at least 120 minutes after each dose of IMP before taking any rescue medication to allow for sufficient time for the IMP to take effect.

Rescue medication (ibuprofen 400 mg, oral, as often as every 6 hours) will be allowed in case of pain due to the dental extraction and will be available to the subject throughout the trial. Ketorolac tromethamine (30 mg, intramuscular, as often as every 4 hours to 6 hours) may be applied as second-line rescue medication at the site if ibuprofen 400 mg fails to relieve pain within 2 hours.

The number of units used, frequency of use, and the observation of any possible adverse event must be reported in the case report form (CRF) and in the source document(s).

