Subjects requiring fourth molar extraction are allowed in the trial. Subjects with molars linked to the mandibular canal and those requiring immediate dental procedures other than third and fourth molar extraction must not be included in the trial.

Postoperative baseline examination and treatment allocation

After surgery, subjects will assess their pain on an 11-point NRS. Subjects who report at least moderate baseline pain intensity (≥ 5 on the NRS) within 4 hours after surgery will be allocated to treatment. If 4 hours elapse without the development of moderate to severe dental pain following the completion of surgery, subjects must not be allocated and must be discontinued from the trial.

The first dose of the IMPs (1 capsule or tablet with active treatment plus 3 placebos) will be administered as soon as subjects report a pain intensity ≥ 5 on the NRS. The time of dosing will be recorded. The use of cold compresses or ice bags on the cheeks of subjects is allowed 4 hours after the administration of IMP; their use must be avoided in the 30-minute period before each pain assessment.

Subjects who undergo surgery and receive IMPs will stay in the dental clinic or other research facility for at least 8 hours after the initial dose and will receive the second dose of IMPs at 8 hours (± 10 minutes). If pain assessments will take place in other research facilities, subjects must be transported to the facility between 15 minutes after the end of surgery and the first IMP administration; the commuting time may be up to 30 minutes. During transfer, subjects must be accompanied by a member of the SMO staff. Both must have written directions in the case of emergency.

Thereafter, they can leave the site and take their third dose of IMPs at home 16 hours (± 1 hour) after the first dose of IMPs. They will be asked to document the intake time and to return for Visit 3 the next day at a time which allows a pain assessment 24 hours after the initial IMP dose was given.

At the site, subjects will be provided with 2 stopwatches and a pain assessment booklet. They will be asked to record their pain assessments during the following 8 hours as follows.

- The baseline pain intensity score (11-point NRS) before the first dose of IMPs (Section 12.2.1.1).
- Pain intensity scores at 15, 30, 45, 60, and 90 minutes (± 2 minutes), and at 2, 3, 4, 5, 6, 7, 8 hours (± 6 minutes) after the first dose of IMPs (Section 12.2.1.1).

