 - Hand out sufficient rescue medication (ibuprofen 400 mg) to cover 24 hours of treatment of dental pain if insufficiently resolved by the intake of IMPs.
 - Hand out an information sheet to the subject with the protocol directions and contact details.
 - Hand out a booklet and ask the subject to document at home:
 - Pain intensity and pain relief at 16 hours.
 - The intake of the third dose of IMPs.
 - Any use of rescue medication.
 - Any use of other medication.
 - Adverse events they might experience.
 - Check that the subjects are in a condition to leave the site.
 - Before subjects leave the site they should be reminded that tramadol-containing products, may impair the mental and/or physical abilities required for the performance of potential hazardous tasks such as driving a car or operating machinery.
 - Ask the subject to come to the site on the next day at a pre-set time (24 hours after first IMP intake) for Visit 3.

Dental clinics must have an emergency kit according to local regulations (Norma Oficial Mexicana NOM-005-SSA3-2010). An emergency crash cart will be mandatory at each research facility any time an IMP is being administered.

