5.6 Review of Blinded Data

A number of analyses may require review of blinded data prior to database lock. The following reviews may occur while the study is ongoing or prior to database lock. Subject ID will be masked in all of these reviews to avoid introducing any bias.

- Concomitant medications are reviewed independent of Subject ID to identify prohibited medications
- Review of adverse event summaries and listings to identify MedDRA preferred terms chosen are consistent with drug's mechanism of action.
- Review of protocol and consent deviations to identify major deviations that would exclude subjects from the per-protocol population.
- Review of subjects with a missing or partial last dose date on the Study Exit Status CRF in order to determine an appropriate imputed date or other missing or partial dates for a parameter of interest; if deemed necessary.
- Reasons for withdrawal which are potentially treatment related

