8.3.1 Analysis of TOTPARs

For the primary endpoint TOTPAR4, as well as for secondary endpoints TOTPAR6 and TOTPAR8, missing pain relief assessments as well as pain relief assessments after start of intake of rescue medication, will be imputed according to the following methods:

1. LOCF with Delta Substitution
 - Last Observation Carried Forward (LOCF) for intermittent missing data and substitution by δ for missing data after premature discontinuation from the trial or disregarded pain relief assessments after start of rescue medication intake. The value of parameter δ will depend on the reason for discontinuation and treatment arm. The following 3 categories of reason for discontinuation will be distinguished: Discontinuation due to Lack of Efficacy (LoE), adverse events, and other, non-drug related reasons. The parameter will be:
 - $\delta = 0$: For missing data after discontinuation due to LoE, discontinuation due to adverse events and for disregarded pain relief assessments after start of rescue medication intake for subjects in the tramadol HCl/diclofenac sodium FDC combination arms
 - $\delta = 0.375$: For missing data after discontinuation due to LoE, discontinuation due to adverse events and for disregarded pain relief assessments after start of rescue medication intake for subjects in the monotherapy arms diclofenac sodium 50 mg and tramadol HCl 50 mg
 - $\delta = 0$: For missing data after discontinuation due to other, non-drug related reasons

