Appendix B: Rules for Censoring in Time to Event Analyses

Below are the detailed rules for determining the time of the event and the censoring times for the various time-to-event analyses to be performed for this study.

Time-to-Event Variable	Event Time Point	Censor Time Point
Time to achieve a 50% reduction of baseline pain	The first time point where pain half gone is indicated, prior to the use of any rescue medication.	Subjects without events are censored at the earlier of the time of their first use of rescue medication and the time of their last, non-missing pain half gone assessment.
Time to onset of first perceptible pain relief*	The time when perceptible pain relief stopwatch is stopped, prior to the use of any rescue medication.	Subjects without events (as indicated by checking the “no” perceptible pain relief box or taking rescue medication prior to the occurrence of perceptible pain relief) are censored at the earlier of the time of their first use of rescue medication, the minutes/seconds entered for time of perceptible pain relief (which is when the stopwatch was stopped and so no longer assessed), and 8 hours.
Time to onset of meaningful pain relief*	The time when meaningful pain relief stopwatch is stopped, prior to the use of any rescue medication.	Subjects without events (as indicated by checking the “no” meaningful pain relief box or taking rescue medication prior to the occurrence of meaningful pain relief) are censored at the earlier of the time of their first use of rescue medication, the minutes/seconds entered for time of meaningful pain relief (which is when the stopwatch was stopped and so no longer assessed), and 8 hours.
Time to intake of first rescue medication dose	The time of first intake of rescue medication within 24 hours of first dose.	Subjects without events are censored at the time of their 24 hour global assessment (at the time when rescue meds were to be turned in), and if one did not take place, then at 24 hours (i.e., when subjects were to turn in their unused rescue medication as Visit 3).
Time to request the first dose of rescue medication	The time of the first request for rescue medication within 24 hours of first dose.	Subjects without events are censored at the time of their 24 hour global assessment (at the time when rescue meds were to be turned in), and if one did not take place, then at 24 hours (i.e., when subjects were to turn in their unused rescue medication as Visit 3).

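### The post-rescue rules react only to trial rescue, so scores after any other analgesic or systemic corticosteroid stay in as observed, mainly in SPID24, the late and peak scores, and time to rescue

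*SAP*

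**What the plan says.** **Trigger.** SAP 8.3 sets the general rule: "Assessments made after the subject's first dose of rescue medication will be considered missing values and excluded from the analyses". SAP 8.3.1 uses the same trigger for the 4-, 6- and 8-hour TOTPARs, in these words: "missing pain relief assessments as well as pain relief assessments after start of intake of rescue medication, will be imputed according to the following methods". The sensitivity methods in SAP 8.3.2, the peak scores in SAP 8.1.3 and the time-to-event rules in SAP Appendix B also depend on rescue. For time to rescue the event is "The time of first intake of rescue medication within 24 hours of first dose". Subjects without that event are censored at their 24-hour global assessment, or at 24 hours if there was none.

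**What counts as rescue.** Protocol 1.4.2: "Rescue medication (ibuprofen 400 mg, oral, as often as every 6 hours) will be allowed in case of pain due to the dental extraction". Ketorolac "may be applied as second-line rescue medication at the site if ibuprofen 400 mg fails to relieve pain within 2 hours". Protocol 12.2.4 derives the amount of rescue used from drug accountability.

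**Other analgesics.** Protocol 1.5 and 10.7 do not allow analgesics or systemic corticosteroids as concomitant medication. Protocol 11.2.1 provides for symptomatic treatment of adverse events and makes no exception for analgesics. The home booklet asks for "Any use of other medication" as an item separate from rescue (Protocol 11.1.2.1), and Protocol 12.1.2 requires all medication to be entered in the CRF. In SAP 5.6, "Concomitant medications are reviewed independent of Subject ID to identify prohibited medications".

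**Consequence of finding such use.** SAP 6 excludes from the PPS subjects with a major deviation affecting the primary endpoint analysis. SAP 9.2.2 repeats only the TOTPARs on the PPS. SAP Appendix C lists the SPID, pain score, peak score and time-to-event tables for the FAS only.

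**The concern.** SAP 8.3.2 explains why post-rescue scores are dropped: pain falls markedly once rescue is given, so later ratings no longer reflect the study drug. That reasoning holds for any analgesic, whoever supplied it. As written, a subject who takes a different analgesic at home keeps every later score at face value and counts as not needing rescue. A subject who takes the dispensed ibuprofen loses the later scores and counts as an event. Two subjects in the same clinical position are handled in opposite ways.

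At stake is the reading of the later secondary endpoints. If subjects with less relief are the ones who reach for something else, the weaker arm would look better on SPID24 and slower to need rescue. The plan also identifies the affected subjects before database lock and then makes no use of that in the analyses most exposed.

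**Working it through.** **1. The plan's own figures.** The documents give no figure for use of other analgesics or its effect. The sample size rests on TOTPAR4 and does not depend on this point. With margin 1.5, SD 4, true difference 0, 1-sided alpha 0.025/4 = 0.00625 and 85% power, the calculation gives 178 per arm against the stated 180.

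**2. Endpoints that home use can reach.** Subjects stay on site for at least 8 hours after the first dose (Protocol 10.2). Each score is weighted by the hours since the previous one (Protocol 12.2.1.3 and 12.2.1.4). Weight on assessments after 8 hours:

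| Endpoint | Hours after 8 h | Share |
|---|---|---|
| TOTPAR4, SPID4 | 0 of 4 | 0% |
| TOTPAR6, SPID6 | 0 of 6 | 0% |
| TOTPAR8, SPID8 | 0 of 8 | 0% |
| SPID24 | 16 of 24 | 67% |

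Peak pain relief runs to 16 hours, and peak pain intensity difference and time to rescue run to 24 hours, so they are exposed too. An analgesic given on site for an adverse event could enter TOTPAR4, TOTPAR6 or TOTPAR8.

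**3. Weight of the 24-hour score.** Pain intensity is rated at 16 hours (Protocol 1.8), but the PID times listed in Protocol 12.2.1.4 and SAP Appendix A go from 8 hours straight to 24. The 24-hour score therefore carries 24 − 16 = 8 hours if the 16-hour score is used, and 24 − 8 = 16 hours on the PID list.

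**4. Illustration on assumed inputs.** Shift in the SPID24 contrast = difference in use × NRS effect × hours. Assume 10% against 5% use and a 24-hour score 3 NRS points lower because of the other drug.
- 16-hour score used: 3 × 8 = 24 points per affected subject; (0.10 − 0.05) × 24 = 1.2 points.
- 16-hour score not used: 3 × 16 = 48 points per affected subject; 0.05 × 48 = 2.4 points.

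Over a wider assumed range, with the effect acting across all 16 hours: 0.02 × 1 × 16 = 0.3 points to 0.10 × 3 × 16 = 4.8 points.

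**5. Scale.** Averaged over the day, 1.2/24 = 0.05 and 2.4/24 = 0.10 NRS points. The largest possible SPID24 is 5 × 24 = 120 for a baseline of 5 and 10 × 24 = 240 for a baseline of 10. So 1.2 points is 0.5% to 1% of it, and 2.4 points is 1% to 2%. The documents give no SD for SPID24, so the shift cannot be set against sampling error.

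**6. Time to rescue.** On the same assumption, and if the affected subjects take no trial rescue, 10% of one arm and 5% of the other are wrongly counted as rescue-free, a 5-percentage-point difference.

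**The case against.** The case against is substantial. Other analgesics are forbidden, subjects are told so, and they have ibuprofen to take home, so such use is a deviation that may be rare. It is recorded, screened blind and classified before lock. SAP 7.2 calls any deviation that impacts efficacy major, and all three TOTPARs are repeated on the PPS. Trial success rests on TOTPAR4 alone. The exposed endpoints serve an exploratory aim and are not adjusted for multiplicity (SAP 9.3). The usage rates above have no source.

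Most of this stands and limits the size of the point, but it does not close the gap. The PPS repeat does not extend to SPID24, the late and peak scores or time to rescue. Home use after 8 hours cannot affect TOTPAR4, so it need not lead to PPS exclusion at all.

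A reader might infer more than the documents support:
- **That home use contaminates TOTPAR6 and TOTPAR8.** It cannot, because both end while subjects are on site.
- **That the problem is confined to later endpoints.** An on-site analgesic for an adverse event before 4 hours would also enter TOTPAR4, where the PPS repeat may partly cover it.
- **That cooling is credited to the drug in the same way.** Protocol 11.1.2.1 says "The use of cold compresses or ice bags on the cheeks of subjects is allowed 4 hours after the administration of IMP", but it bars cooling in the 30 minutes before each assessment. Cooling is open to all blinded arms, and nothing in the documents shows carry-over beyond 30 minutes or different use by arm.
- **That the bias must run toward no difference.** That requires use to differ between arms in a particular direction, and the documents give no rates.

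**Conclusion.** The gap is real and narrow. Followed as written, the SAP keeps scores after a non-trial analgesic or systemic corticosteroid as observed and, absent trial rescue, censors the subject as rescue-free at about 24 hours. This matters mainly for SPID24 (67% of its weight falls after the 8-hour stay), the 16- and 24-hour scores, peak scores and time to rescue, none of which has an analysis that removes such use. The illustrative SPID24 shift of 1.2 to 2.4 points rests on assumed use of 10% against 5% and an assumed 3-point effect. It is small against the scale's range, and its true size and direction are unknown. The documents do not support extending the point to cooling, or reading it as a threat to the trial's primary conclusion. It is worth correcting because the remedy is inexpensive and follows the SAP's own reasoning.

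**What to change.** Before unblinding:
- In SAP 8.3, 8.3.1 and the peak-score rules, define the trigger as the first intake after IMP of trial rescue, or of any other non-IMP analgesic or systemic corticosteroid found in the blinded review. Note the change in SAP 11.
- Confirm that the time of intake is captured. Protocol 12.2.4 requires it for rescue, but neither Protocol 11.1.2.1 nor 12.1.2 states it for other medication.
- Keep time to first trial rescue as defined, since it is a protocol endpoint, and add one sensitivity run with the broader event.
- Add one sensitivity run of SPID24 with the broader event, so that results with and without the affected late scores can be compared.
- Report the number of affected subjects by arm.
- Reconcile Protocol 10.7 (analgesics not allowed) with Protocol 11.2.1 (symptomatic treatment of adverse events). This review takes no position on the clinical rule.

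**Cost.** SAP wording, one derived flag, two extra runs and a check on intake times. A few more subjects are treated as rescued. Because SAP 8.3 imputes only the TOTPARs, the broader trigger also leaves a few more late SPID scores missing with nothing in their place, possibly in subjects with poor relief. This is why SPID24 should be shown both ways. Sample size and the ANCOVA model do not change.
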